5.1.1 Study duration per subject

The total study duration per subject will be up to 24 weeks, including a 4-week Screening Period, a 3-week Titration Period, a 12-week Maintenance Period, a Taper Period of 4 days (with de-escalation by 1 dose step every 2 days), and a 30-day Safety Follow-Up Period (for subjects not participating in the open-label, long-term follow-up study).

The end of the study is defined as the last visit of the last subject in the study.

5.1.2 Planned number of subjects and sites

A total of 138 subjects are planned to be randomized during the study. A remote clinical study model in the USA is planned to be utilized in the study.

5.1.3 Anticipated regions and country

This study will be conducted in the USA.

5.2 Schedule of study assessments

The schedule of study assessments is provided in [Table 5-1](#).

Table 5–1: Schedule of assessments

	Screening Period (+1 day)	Rand (+3 days)	Titration Period ^a (±1 day)			EOT/SOM	Maintenance Period ^a (±2 days)		Taper Period (4 days) ^a		Safety Follow-Up ^a (30 ±5 days)	Un-scheduled Visit ^b
									End of Maintenance ^a /WD Visit	End of Taper		
	V1	V2/BL	V3	V4	V5	V6	V7	V8	V9	V10	Telemedicine Call	
Assessment	Day -28 to Day -1	Day 0	Day 1	Day 8	Day 15	Day 22	Day 50	Day 78	Day 106	Day 110		
Informed consent	X											
Demography	X											
Eligibility criteria	X	X										
Withdrawal criteria		X	X	X	X	X	X	X	X			X
Randomization		X										
General medical/ procedures history	X											
Lifestyle	X											
Reproductive potential and birth control	X											
Brief physical examination	X								X		X	X
Neurological examination	X								X		X	X
C-SSRS	X	X	X	X	X	X	X	X	X	X	X	X ^c
Vital signs	X						X		X		X	X
Body weight, height, and BMI	X						X		X		X	
12-lead ECG	X								X		X	X
Safety laboratory tests	X						X		X		X	X
Urine drug screen	X											X
Pregnancy Test ^d (hCG)	X						X		X		X	X

Table 5–1: Schedule of assessments

	Screening Period (+1 day)	Rand (+3 days)	Titration Period ^a (±1 day)			EOT/SOM	Maintenance Period ^a (±2 days)		Taper Period (4 days) ^a		Safety Follow-Up ^a (30 ±5 days)	Un-scheduled Visit ^b
									End of Maintenance ^a /WD Visit	End of Taper		
	Telemedicine Calls										Telemedicine Call	
	V1	V2/BL	V3	V4	V5	V6	V7	V8	V9	V10		
Assessment	Day -28 to Day -1	Day 0	Day 1	Day 8	Day 15	Day 22	Day 50	Day 78	Day 106	Day 110		
Hormone status	X								X		X	X
PK sampling ^e						X			X			
IRLS	X	X ^f				X	X	X	X			
CGI	X	X				X	X	X	X			
RLS-6		X				X	X	X	X			
mMIDI	X					X			X			X
Menstrual function ^d		X				X			X		X	X
Subject Quality of Life Questionnaire		X				X			X			
Recording of medication and procedures	X	X		X	X	X	X	X	X		X	X
Adverse event assessment	X	X		X	X	X	X	X	X	X	X	X
Contact IRT	X	X				X	X	X	X		X	X
Dispense study medication			X ^g			X ^g	X ^g	X ^g	X ^g			X
Return unused study medication						X	X	X	X		X	X

Table 5–1: Schedule of assessments

	Screening Period (+1 day)	Rand (+3 days)	Titration Period ^a (±1 day)			EOT/SOM	Maintenance Period ^a (±2 days)		Taper Period (4 days) ^a		Safety Follow-Up ^a (30 ±5 days)	Un-scheduled Visit ^b
									End of Maintenance ^a /WD Visit	End of Taper		
	V1	V2/BL	V3	V4	V5	V6	V7	V8	V9	V10		
	Day -28 to Day -1	Day 0	Day 1	Day 8	Day 15	Day 22	Day 50	Day 78	Day 106	Day 110		
Assessment												

BL=Baseline; BMI=body mass index; CGI=Clinical Global Impressions; C-SSRS=Columbia-Suicide Severity Rating Scale; ECG=electrocardiogram; eCRF=electronic Case Report form; EOT=End of Titration; hCG=human chorionic gonadotropin; IRLS=International Restless Legs Scale; IRT=interactive response technology; mMIDI=Modified Minnesota Impulsive Disorder Interview; PK=pharmacokinetic; Rand=randomization; RLS=Restless Legs Syndrome; SOM=Start of Maintenance; V=Visit; WD=withdrawal

Note: The date of informed consent may be prior to screening assessments and study procedures.

Note: Rescreening is allowed with the permission of the Study Physician or representative.

Note: For Visit 2, there is a visit window of +3 days to allow for direct-to-subject shipment of study medication. Visit 3/Day 1 is the first day of study medication exposure. All subsequent visits are calculated based on Visit 3/Day 1.

Note: Visit 6 is the end of the Titration Period and start of the Maintenance Period. Visit 9 is the end of the Maintenance Period and start of the Taper Period.

Note: All visits are via telemedicine calls, with the exception of Visit 1, Visit 6, Visit 9, and SFU. Unscheduled visits are at the discretion of the investigator and may be telemedicine calls.

^a The visit window for Titration Visits is ±1 day per visit relative to Visit 3 (day of first dose). The visit window for visits during the Maintenance Period, including the End of Maintenance Visit, is ±2 days per visit. The Taper Period, which will last up to a maximum of 4 days, will start on the day after the End of Maintenance Visit. The visit window for Safety Follow-Up Period is 30 days±5 days relative to the end of the Taper Period. Following dose de-escalation, subjects may be eligible to participate in the open-label, long-term follow-up study (RL0007) at any time prior to the Safety Follow-Up Visit (see Section 5). The Safety Follow-Up Visit is for subjects not entering RL0007.

^b Assessments to be performed are at the investigator's discretion.

^c C-SSRS is required if the Un-scheduled Visit is conducted due to safety or efficacy reasons.

^d Pregnancy test and menstrual function for all female subjects; serum pregnancy test at Screening and urine pregnancy test at all other visits. A positive urine pregnancy test must be confirmed by a serum pregnancy test.

^e At the time of PK sampling, sampling time, time of application of study medication, and application site of study medication should be recorded in the eCRF.

[figure not shown]
^f At Baseline, subjects must score ≥15 on the IRLS Rating Scale (indicating moderate-to-severe RLS) and must score ≥4 points on the CGI Item 1.

^g Study medication to be shipped to subject's home to be available no later than this date.

5.3 Schematic diagram

Subjects will be randomized to 1 of 3 treatment groups:

Figure 5–1: Schematic diagram

* Two patch sizes will be used: 5cm² and 10cm². Placebo patches will be identical in size and appearance to active patches.

- Subjects will remain at the assigned dose level throughout the 12-week Maintenance Period.
- Subjects will be allowed to back-titrate 1 dose level during the Titration Period. See [Section 5.1](#).
- Subjects will complete the Titration Period at the back-titrated dose level and remain at this dose level for the duration of the Maintenance Period.

5.4 Rationale for study design and selection of dose

SP1006 is a Phase 3, remote, double-blind, randomized, placebo-controlled study of fixed dose administration of the rotigotine transdermal system, designed to investigate the efficacy, safety, and tolerability of rotigotine in adolescent subjects 13 to 17 years of age. The study design is based on the FDA's request to conduct a study in adolescents with RLS. The fixed dose levels of 2mg/24h and 3mg/24h were chosen based on the results of the SP1004 PK/PD study in a similar population.

The PK results of SP1004 were similar compared with those obtained in adults. Rotigotine plasma clearance was similar as compared to adults, although the mean value appeared to be somewhat higher; however, given the high variability, the meaning of this is negligible. Mean volume of distribution, AUC, and C_{max} were similar to results obtained in adults earlier.

In terms of safety, the rotigotine transdermal system was well tolerated at doses of up to 3mg/24h in adolescent subjects with idiopathic RLS. No safety issues were identified in SP1004. A similar number of subjects reported treatment-emergent adverse events (TEAEs) in the 0.5mg/24h, 1mg/24h, and 2mg/24h dose steps during the study, with fewer subjects reporting TEAEs in the 3mg/24h dose step. Overall, 62.5% reported TEAEs, and 45.8% reported drug-related TEAEs. The most frequently reported TEAEs (and drug-related TEAEs) were in the system organ class (SOC) of Gastrointestinal disorders, with nausea the most frequently reported TEAE by preferred term (PT). All of the TEAEs in this study were mild or moderate in intensity. No deaths, serious adverse events (SAEs), or TEAEs leading to discontinuation were reported during the study.

Fourteen subjects from SP1004 were rolled over to open-label extension study SP1005 and were treated for up to 2 years. Overall, rotigotine was well tolerated with long-term use.

Augmentation, defined as an increase in the severity of symptoms beyond baseline levels, represents the main complication of long-term dopaminergic treatment. Augmentation did not occur in SP1004; however, the study was too short to trigger augmentation with less than 5 weeks of treatment in total.

The 2mg/24h and 3mg/24h rotigotine doses chosen for testing in this protocol, SP1006, were selected by balancing the potential need for higher doses with the risk of augmentation as seen in adults receiving doses higher than 3mg/24h. Previous studies have indicated that the incidence of augmentation with rotigotine is low during 6 months and 1 year of treatment. Following an open-label extension study of the long-term safety and efficacy of rotigotine transdermal patch in adult patients with moderate-to-severe idiopathic RLS, a retrospective systematic analysis was conducted in order to investigate the 5-year incidence of augmentation. In this study, the dose was titrated in weekly increments (up to 4 weeks) from 0.5mg/24h to a maximum of 4mg/24h, followed by up to 5 years of maintenance at the optimum dose. Clinically significant augmentation was recorded in 8% of adult patients receiving rotigotine at doses of 4mg/24h compared with 5% of patients receiving rotigotine doses of ≤ 3 mg/24h (Oertel et al, 2011).

6 SELECTION AND WITHDRAWAL OF SUBJECTS

6.1 Inclusion criteria

To be eligible to participate in this study, all of the following criteria must be met:

1. An Institutional Review Board (IRB)/Independent Ethics Committee (IEC) approved written Informed Consent form is signed and dated by the subject or by the parent(s) or legal representative. The Informed Consent form or a specific Assent form, where required, will be signed and dated by minors.
2. Subject/legal representative is considered reliable and capable of adhering to the protocol (eg, able to understand and complete questionnaires), visit schedule, and medication intake according to the judgment of the investigator.
3. Subject is male or female, and is ≥ 13 and < 18 years of age at Baseline.
4. Subject weighs ≥ 40 kg.
5. Deleted.
6. Subject meets the diagnosis of RLS based on all of the following features according to the 2013 Revised International RLS Group Diagnostic Criteria (Pichietti et al, 2013):
 - An urge to move the legs usually, but not always, accompanied by or felt to be caused by uncomfortable and unpleasant sensations in the legs (sometimes the urge to move the legs is present without the uncomfortable sensations and sometimes the arms or other parts of the body are involved in addition to the legs. For children, the description of these symptoms should be in the child's own words.).
 - The urge to move the legs and any accompanying unpleasant sensations begin or worsen during periods of rest or inactivity such as lying down or sitting.
 - The urge to move the legs and any accompanying unpleasant sensations are partially or totally relieved by movement, such as walking or stretching, at least as long as the activity continues (when symptoms are very severe, relief by activity may not be noticeable but must have been previously present).
 - The urge to move the legs and any accompanying unpleasant sensations during rest or inactivity only occur or are worse in the evening or night than during the day (when symptoms are very severe, the worsening at night may not be noticeable but must have been previously present).
 - The occurrence of the above features is not solely accounted for as symptoms primary to another medical or behavioral condition (eg, myalgia, venous stasis, leg edema, arthritis, leg cramps, positional discomfort, habitual foot tapping).
7. Subject's RLS symptoms cause significant daytime symptoms or significant distress or impairment in social, occupational, educational, or other important areas of functioning by the impact on sleep, energy/vitality, daily activities, behavior, cognition or mood.
8. At Baseline, subject has a score of ≥ 15 on the IRLS Rating Scale (indicating moderate-to-severe RLS).
9. At Baseline, subject scores ≥ 4 points on the CGI Item 1 assessment (indicating at least moderately ill).
- 10a. Subjects who are receiving supplemental iron have been on a stable dose for at least 1 month prior to Screening. Subjects previously treated with supplemental iron must have a

washout period of at least 1 month prior to Screening. No supplemental iron administration or iron dose adjustment will be allowed while in study, unless medically necessary.

11. Female subjects must be surgically incapable of childbearing, or effectively practicing an acceptable method of contraception (oral/parenteral/implantable hormonal contraceptives, intrauterine device, or barrier and spermicide). Abstinence is an acceptable method. Subjects must agree to use adequate contraception during the study and for 4 weeks after their final dose of study medication.

6.2 Exclusion criteria

Subjects are not permitted to enroll in the study if any of the following criteria is met:

1. Subject has previously participated in this study or subject has received previous treatment with rotigotine.
2. Subject has participated in another study of an IMP or a medical device within the last 3 months prior to Visit 1/Screening or is currently participating in another study of an IMP or a medical device.
3. Subject has clinically relevant renal dysfunction (serum creatinine >1.5 mg/dL) at Visit 1/Screening.
- 4a. Subject has a serum ferritin level below the lower limit of normal at Visit 1/Screening.
5. Subject has a hemoglobin level below the lower limit of normal at Visit 1/Screening.
6. Subject has had previous treatment with dopamine agonists or L-dopa within 7 days prior to Visit 2/Baseline.
7. Subject has any medical or psychiatric condition, which in the opinion of the investigator, would jeopardize or compromise the subject's well-being or ability to participate in this study.
8. Subject is pregnant or nursing.
9. Subject is not willing to abstain from caffeine after 4pm each evening within 7 days prior to Visit 2/Baseline and for the duration of the study.
10. Subject has a QTc interval of ≥ 500 ms at Visit 1/Screening. Bazett's correction method must be used for the correction of the QT interval.
11. At Visit 1/Screening, subject has symptomatic orthostatic hypotension with a decrease of blood pressure (BP) from supine to standing position of ≥ 20 mmHg in systolic blood pressure (SBP) or of ≥ 10 mmHg in diastolic blood pressure (DBP) taken from the 5 minute supine and 1 and/or 3 minute standing measurements.
12. Subject has a known hypersensitivity to any of the components of the study medication, such as a history of significant skin hypersensitivity to adhesives, known hypersensitivity to other transdermal medications or has unresolved contact dermatitis or eczema.
13. Subject has secondary RLS (eg, due to renal insufficiency [uremia], iron deficiency, or rheumatoid arthritis).

14. Subject has a lifetime history of suicide attempts (including actual attempt, interrupted attempt, or aborted attempt), or had suicidal ideation in the past 6 months as indicated by a positive response (“Yes”) to either Question 4 or Question 5 of the C-SSRS at Screening (Visit 1).
15. Subject is taking a prohibited concomitant medication (see [Section 7.8.2](#)). Prohibited concomitant medication must have been discontinued at least 2 weeks prior to Screening (Visit 1).

6.3 Withdrawal criteria

Subjects are free to withdraw from the study at any time, without prejudice to their continued care. Subjects should be withdrawn from the study if any of the following events occur:

1. Subject develops a physical or mental illness or AE that would interfere with his/her continued participation.
2. Subject is noncompliant with the study procedures or medications in the opinion of the investigator.
3. The investigator feels that it is in the subject’s best interest to withdraw from the study.
4. Subject is unwilling to manage the application and removal of patches at any time during the study.
5. The subject develops clinically relevant symptomatic orthostatic hypotension.
6. The subject develops a clinically relevant ECG abnormality that is confirmed by a repeat ECG performed at least 1 hour later. If abnormalities are still present, the subject is to be withdrawn from the study.
7. The subject has a QTc interval ≥ 500 ms and/or a QTc interval which has increased by ≥ 60 ms as compared to the QTc interval taken at Visit 1/Screening. Bazett’s method must be used for correction of QT intervals.
8. Subject or parent(s)/legal representative withdraws his or her consent.
9. There is confirmation of a pregnancy during the study, as evidenced by a positive pregnancy test.
10. The sponsor or a regulatory agency requests withdrawal of the subject.
11. Subject has active suicidal ideation as indicated by a positive response (“Yes”) to either Question 4 or Question 5 of the “Since Last Visit” version of the C-SSRS. The subject should be referred immediately to a Mental Healthcare Professional and must be withdrawn from the study.

Investigators/designated study staff should attempt to obtain information on subjects in the case of withdrawal or discontinuation. For subjects considered as lost to follow up, the investigator/designated study staff should make an effort (at least 1 phone call and 1 written message to the subject), and document his/her effort (date and summary of the phone call and copy of the written message in the source documents), to complete the final evaluation. All results of these evaluations and observations, together with a narrative description of the

reason(s) for removing the subject, must be recorded in the source documents. The eCRF must document the primary reason for withdrawal or discontinuation.

Investigators should contact the Medical Monitor, whenever possible, to discuss the withdrawal of a subject in advance.

6.3.1 Potential drug-induced liver injury IMP discontinuation criteria

Subjects with potential drug-induced liver injury (PDILI) must be assessed to determine if IMP must be discontinued. In addition, all concomitant medications and herbal supplements that are not medically necessary should also be discontinued.

The PDILI criteria below require immediate and permanent discontinuation of IMP:

- Subjects with either of the following:
 - ALT or AST $\geq 5xULN$
 - ALT or AST $\geq 3xULN$ and coexisting total bilirubin $\geq 2xULN$

The PDILI criterion below requires immediate discontinuation of IMP:

- Subjects with ALT or AST $\geq 3xULN$ who exhibit temporally associated symptoms of hepatitis or hypersensitivity. Hepatitis symptoms include fatigue, nausea, vomiting, right upper quadrant pain or tenderness. Hypersensitivity symptoms include fever (without clear alternative cause), rash, or eosinophilia (ie, $>5\%$).

If a nondrug-related cause for the symptoms can be confirmed, these subjects may resume IMP administration after discussion with the responsible UCB physician, but only when the requirements for rechallenge with IMP as provided in [Section 11.6.1.2](#) are followed.

The PDILI criterion below allows for subjects to continue on IMP at the discretion of the investigator.

- Subjects with ALT or AST $\geq 3xULN$ (and $\geq 2x$ baseline) and $<5xULN$, total bilirubin $<2xULN$, and no eosinophilia (ie, $\leq 5\%$), with no fever, rash, or symptoms of hepatitis (eg, fatigue, nausea, vomiting, right upper quadrant pain or tenderness).

Evaluation of PDILI must be initiated as described in [Section 11.6.1](#). If subjects are unable to comply with the applicable monitoring schedule, IMP must be discontinued immediately.

Investigators should attempt to obtain information on subjects in the case of IMP discontinuation to complete the final evaluation. Subjects with PDILI should not be withdrawn from the study until investigation and monitoring are complete. All results of these evaluations and observations, as well as the reason(s) for IMP discontinuation and subject withdrawal (if applicable), must be recorded in the source documents. The eCRF must document the primary reason for IMP discontinuation.

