When IMP is stopped due to PDILI (as described in [Section 6.3.1](#)), IMP must be permanently discontinued unless a subsequent alternative diagnosis fully explains the hepatic findings.

Rechallenge with a substance potentially causing drug-induced liver injury is dangerous, may be fatal, and must not occur.

The table below summarizes the approach to investigate PDILI.

Table 11–3: Required investigations and follow up for PDILI

Laboratory value			Immediate		Follow up	
ALT or AST	Total bilirubin	Symptoms ^a of hepatitis or hypersensitivity	Consultation requirements	Actions	Testing	Evaluation
≥3xULN	≥2xULN ^b	NA	Hepatology consult. ^c	Immediate, permanent IMP discontinuation.	Essential: Must have repeat liver chemistry values and additional testing completed ASAP (see Section 11.6.1.3).	Monitoring of liver chemistry values at least twice per week until values normalize, stabilize, or return to within baseline values. ^d
≥8xULN	NA	NA	Medical Monitor must be notified within 24 hours (eg, by laboratory alert) and subject discussed with Medical Monitor ASAP.			
≥3xULN	NA	Yes		Immediate, temporary or permanent, IMP discontinuation.		
≥3xULN (and ≥2x baseline) and <5xULN	<2xULN	No	Discussion with Medical Monitor required if the criterion that allows for IMP continuation is met.	Further investigation – immediate IMP discontinuation not required (see Section 11.6.1.2).	Not required unless otherwise medically indicated (at discretion of investigator).	
≥5xULN (and ≥2x baseline)	<2xULN	No	Discussion with Medical Monitor required.	Immediate, permanent IMP discontinuation.	Essential: Every attempt must be made to have repeat liver chemistry values and additional testing completed within 48 hours (see Section 11.6.1.3).	Monitoring of liver chemistry values at least twice per week until values normalize, stabilize, or return to within baseline values. ^d

Table 11–3: Required investigations and follow up for PDILI

Laboratory value			Immediate		Follow up	
ALT or AST	Total bilirubin	Symptoms ^a of hepatitis or hypersensitivity	Consultation requirements	Actions	Testing	Evaluation

ALP=alkaline phosphatase; ALT=alanine aminotransferase; ASAP=as soon as possible; AST=aspartate aminotransferase; IMP=investigational medicinal product; NA=not applicable; PDILI=potential drug-induced liver injury; ULN=upper limit of normal

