11.6.1.2 Immediate action: determination of IMP discontinuation

All PDILI events require immediate action, testing, and monitoring.

The immediate action is dependent on the laboratory values and symptoms of hepatitis or hypersensitivity and ranges from continuation of IMP (followed by immediate investigation) to immediate and permanent discontinuation (see [Section 6.3.1](#) and [Table 11-3](#) for details).

When IMP is discontinued, all concomitant medications and herbal supplements that are not medically necessary should also be discontinued. The investigator should also consider dose reduction for medically necessary concomitant medication and consider changing any medically required concomitant medication known to be hepatotoxic to a suitable alternative.

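### Liver stopping and restart rules disagree in a narrow band (ALT/AST 5 to <8xULN, bilirubin <2xULN), and the restart sentence in Protocol 6.3.1 cites requirements that 11.6.1.2 does not contain

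*Protocol*

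**What the plan says.** **Protocol 6.3.1** sets three tiers.

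- Under "The PDILI criteria below require immediate and permanent discontinuation of IMP" it lists ALT or AST at or above 5xULN, and ALT or AST at or above 3xULN with bilirubin at or above 2xULN.
- A second tier requires immediate discontinuation at or above 3xULN with symptoms of hepatitis or hypersensitivity. It states no upper limit for ALT/AST and none for bilirubin. Its restart sentence is "If a nondrug-related cause for the symptoms can be confirmed, these subjects may resume IMP administration after discussion with the responsible UCB physician, but only", continuing "but only when the requirements for rechallenge with IMP as provided in" Section 11.6.1.2.
- A third tier lets asymptomatic subjects at 3 to <5xULN, at least twice baseline and with bilirubin <2xULN, continue at the investigator's discretion.

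**Protocol 11.6.1** opens by naming 6.3.1 as the place where the discontinuation criteria are given. For any stop made under 6.3.1 it then says "IMP must be permanently discontinued unless a subsequent alternative diagnosis fully explains the hepatic findings", and adds that a potentially causative substance must not be given again.

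**Table 11-3** has a symptomatic row at or above 3xULN, again without an upper limit, with the action "Immediate, temporary or permanent, IMP discontinuation". Its asymptomatic permanent-stop row applies only at "≥5xULN (and ≥2x baseline)" with bilirubin <2xULN.

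**Protocol 11.6.1.2** says the action "ranges from continuation of IMP (followed by immediate investigation) to immediate and permanent discontinuation" and refers to both 6.3.1 and Table 11-3 for details. The rest concerns concomitant medication.

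**SAP 10.3.1** defines potential Hy's Law with an ALP limit of 2 and no unit. Protocol 11.1.1.3 uses 2xULN.

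**The concern.** These are stopping and restart rules for adolescents on an investigational drug, and they are written in several places that do not fully match. In Table 11-3, within the band 5 to <8xULN and bilirubin <2xULN, adding symptoms of hepatitis turns a permanent stop into one that may be temporary. That is hard to defend as intended. The symptoms include nausea, which Protocol 5.4 reports as the most frequent treatment-emergent event in the earlier adolescent study, so once transaminases are raised the symptomatic row is not a remote case.

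The restart sentence has a separate problem. It asks about the cause of the symptoms, whereas 11.6.1 asks about the liver results, and the safeguard it relies on is not at the place cited. Someone working from 6.3.1 alone would see a weaker test than the protocol intends. Someone working from the table alone could treat as temporary a stop that 6.3.1 makes permanent.

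**Working it through.** The plan gives no figure to reproduce. The check applies both sets of rules to the same subject.

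**Step 1: permanent stop at or above 5xULN.** Section 6.3.1 says permanent in every line below.

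| ALT/AST (xULN) | Bilirubin (xULN) | Symptoms | Relative to baseline | Table 11-3 |
|---|---|---|---|---|
| ≥8 | any | any | any | permanent row matches |
| 5 to <8 | ≥2 | any | any | permanent row matches |
| 5 to <8 | <2 | no | ≥2x | permanent row matches |
| 5 to <8 | <2 | no | <2x | no row matches |
| 5 to <8 | <2 | yes | any | only the temporary-or-permanent row matches |

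The first line assumes that the permanent-stop action covers both the bilirubin row and the ≥8xULN row. The extracted table is broken there, and this is the natural reading. In the first two lines a symptomatic subject also matches the temporary-or-permanent row; I take the specific permanent row to prevail.

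**Step 2: extent on a grid.** ALT/AST runs from 5 to 9xULN in steps of 0.5 (9 values), baseline from 0.5 to 4xULN in steps of 0.5 (8 values), bilirubin is 1 or 2xULN (2), symptoms yes or no (2).

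- Cells: 9 × 8 × 2 × 2 = 288, all permanent under 6.3.1.
- Symptomatic, bilirubin 1xULN, ALT/AST 5.0 to 7.5xULN: 6 × 8 = 48 cells, temporary-or-permanent only.
- Asymptomatic, bilirubin 1xULN, same ALT/AST values, below twice baseline: 3 + 3 + 2 + 2 + 1 + 1 = 12 cells, no row.
- Agreement: 288 − 48 − 12 = 228 cells.

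The counts depend on the step sizes and show only where the rules part. The asymptomatic gap needs ALT/AST ≥5xULN and below twice baseline, so baseline must exceed 5/2 = 2.5xULN. That is uncommon, but it is not excluded by a numerical limit. Section 6.2 sets laboratory limits for creatinine, ferritin and hemoglobin ("Subject has a hemoglobin level below the lower limit of normal at Visit 1/Screening") and none for ALT or AST, although the investigator-judgment exclusion could still apply.

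**Step 3: overlap inside 6.3.1.** Take ALT 6xULN, bilirubin 1xULN and vomiting. Because 6 ≥ 5, the permanent tier applies. Because 6 ≥ 3 with symptoms, the symptomatic tier and its restart sentence also apply. The section does not say which prevails.

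**Step 4: restart test.**

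| | 6.3.1 | 11.6.1 |
|---|---|---|
| What must be explained | the symptoms | the hepatic findings |
| Standard | nondrug cause confirmed | alternative diagnosis explains them fully |
| Further condition | sponsor physician discussion; requirements in 11.6.1.2 (none there) | no re-exposure to a potentially causative substance |

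A subject at 4xULN whose vomiting has a confirmed nondrug cause, but whose transaminases remain unexplained, passes the first test and fails the second. The 11.6.1 exception is also written for any stop under 6.3.1, so read literally it reaches the permanent-stop group too.

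**Step 5: SAP limit.** Assume ALP in U/L with a ULN of 100 to 500 U/L. The protocol cut is then 200 to 1000 U/L, while a literal 2 U/L is 2/100 = 0.02 down to 2/500 = 0.004xULN, which no realistic value would meet. A subject with ALT 6xULN, bilirubin 2.5xULN and ALP 1xULN meets the protocol's biochemical thresholds and has nR = 6/1 = 6, in the SAP's hepatocellular class (≥5), yet would be missed.

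**The case against.** The strongest reply is that the documents rank themselves. Section 11.6.1 names 6.3.1 as the source of the discontinuation criteria, and Table 11-3 is presented as a summary of investigation and follow-up. The table's symptomatic action includes a permanent stop, so an investigator who stops permanently at 5 to <8xULN complies with both texts, and both require dosing to stop at once. Section 11.6.1.1 requires Medical Monitor notification within 24 hours and discussion as soon as possible, so nobody should be acting on one table row alone. All of this stands, and it makes the practical divergence small. It does not remove the mismatch, because 11.6.1.2 sends the reader to both sources for the immediate action and gives no order of precedence.

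Three stronger readings are tempting and not supported.

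- A reader might infer that the protocol allows restart on a symptom explanation alone. It does not: 11.6.1 governs every stop made under 6.3.1 and requires the liver findings to be fully explained.
- A reader might infer that Table 11-3 generally overrides the 5xULN stop or lets dosing continue. It agrees with 6.3.1 outside the band, and within it no row allows dosing to continue.
- A reader might infer that the SAP would lose Hy's Law cases. The other limits in that sentence are in ULN multiples and the nR formula divides ALP by its ULN, so the intended unit is evident. Even a literal reading leaves the wider elevated-liver-test listing, the flagged laboratory listings and the special-interest event reporting in place.

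**Conclusion.** The concern holds in a narrow form. The stopping rules conflict only at ALT/AST 5 to <8xULN with bilirubin <2xULN, and then only for symptomatic subjects or asymptomatic subjects below twice baseline. Section 6.3.1 has an unresolved overlap between its symptomatic and permanent tiers. The restart defect is a dead cross-reference and a test that is weaker when read alone; with 11.6.1 the stricter test governs. The SAP omission is clerical and touches only a listing's Hy's Law identification and nR.

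This rests on reading the permanent action as covering the ≥8xULN row and on a specific permanent row prevailing where two rows match. The documents report no liver enzyme elevations, so the frequency of such cases is unknown. There is no effect on efficacy, alpha or power. SAP Section 1 records early termination, so the protocol points matter only for further use or reuse of this text. Whether the SAP line can still change an output depends on database-lock status, which the documents do not give.

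**What to change.** - In both 6.3.1 and Table 11-3, limit the symptomatic criterion with temporary or permanent discontinuation to ALT/AST ≥3 to <5xULN with bilirubin <2xULN.
- In Table 11-3, make the permanent stop at ≥5xULN unconditional on symptoms and baseline. All 288 grid cells then give a permanent stop, and the symptomatic row no longer overlaps a permanent one.
- In 6.3.1, replace the symptom-based restart test and the reference to 11.6.1.2 with the 11.6.1 condition, and keep the discussion with the sponsor's physician.
- In 11.6.1, state that the restart exception applies only to the symptomatic group below 5xULN.
- In SAP 10.3.1, write the ALP limit as <2xULN, matching Protocol 11.1.1.3. If the listing has already been produced, check the programmed cut.

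The cost is wording only, with no new procedures, data or analyses.
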